The power analysis was calculated conservatively for the following hypotheses:

Hypothesis 1: Nausea scores on the BARF and VAS scales would be lower in children after the administration of an antiemetic. A reduction in the VAS by 2 cms and by 1 face on a faces scale is considered a clinically important reduction in symptoms. (13) Assuming that the SD of nausea on the VAS scale in children is similar to that in adults (2.5 cm) (14), a sample size of 27 would have a 90% power at the 0.01 level of significance in detecting a 2.0 cm difference in the VAS following antiemetic therapy. Hypothesis 2: Children who received rescue antiemetics in the postoperative period will have higher postoperative nausea scores on the BARF and VAS scales than those who did not receive rescue antiemetics. In addition, children who required rescue antiemetics will have higher nausea scores at the time they received the rescue drug in the postoperative period than before they developed nausea. In other words, nausea scores in the postoperative period will be higher than scores prior to induction of anesthesia in children who received rescue antiemetics. (12) The power analysis for hypothesis 2 is similar to that for hypothesis 1, and a sample size of 27 would have a 90% power at the 0.01 level of significance in detecting a 2.0 cm difference in the VAS.

Hypothesis 3: There will be a good correlation between the BARF and VAS scores for nausea. A sample size of 127 would be estimated for an estimated maximum r of 0.8, a half-width of the confidence interval of ± 0.1 at an alpha of 0.01. (15) These estimates of r are in keeping with previous studies of the correlation between

pain scores on the VAS and the FPS-R scales. (6)

Allowing for a 10% rate of dropouts and incomplete data, we plan to recruit 240 patients in the preoperative area for the study to obtain data to test all hypotheses.

G2. Data Analysis

Provide a description of your plan for data analysis. State the types of comparisons you plan (e.g. comparison of means, comparison of proportions, regressions, analysis of variance). Which is the PRIMARY comparison/analysis? How will the analyses proposed relate to the primary purposes of your study?

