Visual analogue scores for pain and for nausea, and FPS-R scores for pain and BARF scores for nausea will be examined for normal distribution by the Kolmogorov-Smirnov test, but it is anticipated that the distribution will not be normal. Descriptive statistics (mean, median, standard deviation, and frequency distribution) of the nausea and pain scores will be obtained. The incidence of postdischarge nausea will be determined from the responses recorded in the diary and in the follow up phone call. The construct validity of the BARF scale would be assessed using the assumption that antiemetics reduce nausea and therefore nausea scores would be lower in children after the administration of an antiemetic (hypothesis 1). A subgroup of patients who received rescue antiemetics in the PACU will be examined. The pretreatment and post treatment VAS scores for nausea and BARF scores will be compared using a Wilcoxon test for non Gaussian distributed data. A reduction of scores by 2 cm on the VAS scale for nausea is traditionally accepted as a clinically satisfactory therapeutic response. A significant reduction in the BARF scores by 1 face in such patients will be accepted as construct validation. Content validity would be assessed by testing the hypothesis is that children with nausea will score higher on these scales than children without nausea (hypothesis 2). We will compare the postoperative nausea scores in patients who received rescue antiemetic therapy with the scores in patients who did not require this therapy using the Mann Whitney test. In addition, we will compare preoperative and postoperative BARF and VAS scores for nausea in patients who received antiemetics, making the assumption that healthy children will be free from nausea in the preoperative area. The Wilcoxon test for non Gaussian distributed data will be used for this comparison. Convergent validity would be tested by examining the correlation between BARF and VAS scales for nausea using the Spearman's Rho test. The hypothesis tested is that there would be a good correlation between the two scales (hypothesis 3). Discriminant validity would be tested by examining the relationship between pain and nausea. The hypothesis tested is that there would be a poor correlation between pain and nausea scores, particularly after the administration of opioids for analgesia (hypothesis 4). The correlation between (1) VAS scores for pain and nausea and (2) pain scores using the FPS-R scale and nausea scores using the BARF scale will be determined. Discriminant validity would be accepted if the correlation between these scores is not as good as the correlation between (a) VAS score for pain and the FPS score, (b) VAS score for nausea and the BARF score. A subgroup of patients who received analgesic therapy in the PACU will be examined. The correlation between the change in pain scores and nausea scores with analgesic treatment will be examined using the Spearman's Rho test. We can anticipate that there will be some correlations between nausea and pain as patients with pain often have concomitant nausea. However, satisfactory treatment of pain with opioids may not reduce nausea but even increase it, as nausea is a side effect of such therapy. Similarly, the correlation between the change in pain scores and nausea scores with antiemetic treatment will be examined using the Spearman's Rho test. The hypothesis tested will be accepted if the correlation of VAS and FPS-R scores will differ from the correlation between VAS scores for nausea and BARF scores. P values below 0.05 will be considered statistically significant. The minimum clinically relevant change in BARF and VAS scores for nausea will be determined by calculating the change in scores for patients who rated their nausea to be a little better than before or a little worse than before. Similarly, the scores at which a patient felt the need for rescue therapy would be determined in those subjects who responded positively to a question "Do you want any treatment for your nausea?" This will provide the threshold score for patient perception of the need for rescue therapy. The first and subsequent scores obtained from subjects who rated their symptoms as "no change from before" will be examined using an intra-class coefficient >0.7 as the criterion for test / retest reliability.

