
Section H: Potential Risks/Discomforts

Describe and assess any potential risks/discomforts; (physical, psychological, social, legal, or other) and assess the likelihood and seriousness of such risks:

The study will not involve any changes in surgical or anesthetic management of the child. Previous studies of pain and nausea in the postoperative period have not shown that repeated questioning of the patient for these symptoms has resulted in increased self reporting of pain or nausea scores and increased rescue therapy. It

is therefore unlikely that the use of the pain and nausea scales will result in unnecessary therapy. The potential risk of this study includes a breach in confidentiality. All research data will be kept secured and locked up in the office of the research co-ordinator. This office is located inside the office of the Department of Anesthesiology at Texas Children's Hospital. This office is only accessible by a personal digital access cards. Unauthorized individuals would not be able to enter these facilities. Any electronic data will be kept in password protected network controlled by the IT department at the Texas Children's Hospital, Department of Anesthesiology. Paper copies of data forms will be stored in a locked cabinet in the Pediatric Anesthesiology office. Electronic files will be maintained on password secured computers. Data will be coded. The likelihood of such events is minimal.

Section I: Potential Benefits

Describe potential benefit(s) to be gained by the individual subject as a result of participating in the planned work.

Patients will not have any direct immediate benefits from participating in these studies

Describe potential benefit(s) to society of the planned work.

Determining the validity of a faces pain scale for Spanish speaking subjects will extend the ability of physicians to use this instrument to rate the severity and need for treatment of subjective symptoms to this population rather than being limited to English speaking subjects.

Do anticipated benefits outweigh potential risks? Discuss the risk-to-benefit ratio.

The minimal risks of loss of confidentiality data is exceeded by the potential benefits to society by demonstrating the clinical utility of a validated tool for measuring nausea in children.

Section J: Consent Procedures

J1. Waiver of Consent

Will any portion of this research require a waiver of consent and authorization?

NA

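### The minimum clinically relevant change is never set against measurement error, so the plan cannot show whether it is detectable in one child

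*Combined protocol and SAP*

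**What the plan says.** Section D lists the minimal clinically relevant difference on the BARF and VAS as objective 3, and test-retest reliability when nausea is unchanged as objective 5. F2 collects repeated nausea scores and a five-level rating of change that includes 'the same', 'a little better' and 'a little worse'.

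G2 turns these data into two separate analyses:

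- **Objective 3.** The minimum relevant change "will be determined by calculating the change in scores for patients who rated their nausea to be a little better than before", with slight worsening handled likewise. G2 names no summary statistic, interval or comparison group.
- **Objective 5.** Repeat scores from children reporting no change "will be examined using an intra-class coefficient >0.7 as the criterion for test / retest reliability".

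Three other statements bear on the point:

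- G1 on the spread of VAS scores: "Assuming that the SD of nausea on the VAS scale in children is similar to that in adults (2.5 cm").
- G1 on what counts as important: "A reduction in the VAS by 2 cms and by 1 face on a faces scale is considered a clinically important reduction in symptoms". G2 repeats the VAS figure: "A reduction of scores by 2 cm on the VAS scale for nausea is traditionally accepted as a clinically satisfactory therapeutic response".
- Section I, which expects physicians to use the instrument to "rate the severity and need for treatment of subjective symptoms".

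**The concern.** Children who say their nausea is the same show how far a score moves when nothing has changed. That is the natural yardstick for the change scored by children who say 'a little better' or 'a little worse'. The plan collects both groups and never puts them side by side.

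The ICC does not fill the gap. It is a ratio of between-child variance to total variance, so it depends on how widely the children differ. It does not say, in centimetres or faces, how large a change must be before it can be told from error. A scale can pass a bar of 0.7 with an error band wider or narrower than the reported change, and nothing planned in G2 would show which.

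Two things are at stake. If the result is offered as a threshold for judging change in one child, it may lie inside that child's measurement error. And if scores drift between ratings for reasons unrelated to nausea, the raw change in the 'a little' groups absorbs the drift unseen.

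**Working it through.** **Inputs**

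- VAS SD 2.5 cm (G1, an adult value assumed to hold in children).
- ICC 0.70, the lowest value at the pass bar (G2).
- Change called important: 2 cm on the VAS (G1, G2).
- 95% multiplier 1.96. This is an assumption, since the documents define no error band.

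**Reproducing the plan's own figure.** For hypothesis 1, G1 states that "a sample size of 27 would have a 90% power at the 0.01 level of significance in detecting a 2.0 cm difference in the VAS". A two-sided paired t-test with difference 2.0 cm, SD 2.5 cm and alpha 0.01 gives n = 27 with 90.5% power, so the figure reproduces. It does so with 2.5 cm as the SD of the paired difference, whereas the text calls it the SD of nausea scores. The SD of a difference is SD × √(2(1 − ρ)), so the two readings agree if the pre-post correlation ρ is 0.5. The steps below follow the text and treat 2.5 cm as the SD of scores.

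**Error band for one child's change between two ratings**

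- Standard error of measurement: SD × √(1 − ICC) = 2.5 × √0.30 = 1.37 cm.
- SD of the difference between two ratings from error alone: √2 × 1.37 = 1.94 cm.
- 95% smallest detectable change: 1.96 × 1.94 = ±3.8 cm, which is 3.8/2 = 1.9 times the 2 cm figure.
- Share of unchanged children moving 2 cm or more in either direction, if error is normal: 2 × (1 − Φ(2/1.94)) = about 30%.
- ICC at which the band falls to 2 cm, with SD 2.5 cm: 1 − (2/(1.96 × √2 × 2.5))² = about 0.92.

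**Sensitivity to the SD, at ICC 0.70.** The band is 1.96 × √0.6 × SD = 1.52 × SD.

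| SD (cm) | 95% smallest detectable change (cm) |
|---|---|
| 1.0 | 1.5 |
| 1.5 | 2.3 |
| 2.0 | 3.0 |
| 2.5 | 3.8 |
| 3.0 | 4.6 |

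The band drops below 2 cm once the SD is below 2/1.52, or about 1.3 cm.

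**Sensitivity to the ICC, at SD 2.5 cm.** The band is 3.1 cm at ICC 0.80, 2.2 cm at 0.90 and 1.55 cm at 0.95.

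**Error in a group mean.** At SD 2.5 cm and ICC 0.70 the 95% half-width is 1.96 × 1.94/√n: 1.2 cm with 10 children, 0.85 cm with 20 and 0.73 cm with 27. The documents do not say how many children are expected in each 'a little' group.

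**BARF.** The documents give no SD in faces, so no matching calculation is possible.

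**The case against.** The strongest reply is that the planned estimate is a recognised anchor-based one and that random error does not bias it. Averaged over a group, individual error shrinks, as the half-widths above show. This stands. A reader might infer from ±3.8 cm that the planned estimate is wrong or is mostly noise. The documents do not support that, because the smallest detectable change answers a different question, about one child.

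The SD is also open to challenge. It is an adult value brought in for the antiemetic comparison. F1 requires children to be free of nausea for the previous 24 hours, and G2 assumes they have none before surgery. Children who then report no change may therefore cluster near zero. At SD 1.0 cm the band is 1.5 cm and only about 1% of unchanged children would move 2 cm or more. This stands too, and it is a reason to estimate the error from the study's own unchanged children.

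The 2 cm figure belongs to hypothesis 1, a group comparison before and after treatment. A reader might infer that the study will publish about 2 cm or 1 face as the minimum relevant change and count that as a success. The documents do not say so. Objective 3 is estimated from data with no preset value, and G2 sets a pass mark for the ICC only.

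Use on one child's change is likewise inferred. Section I speaks of rating severity and need for treatment, which are ratings at one time, and need for treatment has its own threshold analysis in G2. The inference is reasonable for a bedside scale, but the text does not state it.

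Finally, the error-band calculation assumes no systematic shift, so it gives no support for comparing the 'a little' groups with the unchanged group. That comparison rests on a separate reason: it is how drift would be seen. None of these replies supplies the missing comparison with measurement error.

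**Conclusion.** The concern holds in a limited form. G2 as written cannot show whether the minimum relevant change on either scale exceeds measurement error in one child, because the unchanged children are used only for an ICC.

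The ±3.8 cm figure is an illustration for the VAS. It needs the adult SD of 2.5 cm to apply to unchanged children, the ICC to sit at its 0.70 minimum, roughly normal error (G2 expects non-normal scores) and no systematic shift. It is the worst case that still passes the bar at that SD, and a half-width for one child. Under other plausible inputs the band runs from below 2 cm to well above it. It should not be read as a statement that the VAS fails to detect 2 cm, and it says nothing numerical about one face on the BARF.

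Validity hypotheses 1 to 4 and the sample size are unaffected. The change is worth making before analysis because it decides whether the result of a listed objective can be offered for individual children or only as a group figure.

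**What to change.** Add to G2, for the BARF and the VAS separately:

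1. From the children who report no change, report the standard error of measurement and the smallest detectable change beside the ICC. Given the expected non-normality, limits of agreement are an alternative.
2. Report the change for 'a little better' and for 'a little worse' separately, never pooled as signed changes, since opposite signs would cancel. Give each with a confidence interval and beside the change in the unchanged group, so that any systematic drift is visible.
3. Describe the result as a threshold for an individual child only where it exceeds the smallest detectable change. Otherwise describe it as a group-level figure.

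The cost is a few lines of text and a minor extra analysis. F2 already collects the five-level rating and the repeat scores, so no new subjects or assessments are needed. The downside is that the reported claim may become less favourable.

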Pediatric research in the management of nausea has been limited by the absence of a reliable method to quantify the intensity of this subjective symptom. In adults, the visual analog scale (VAS) is an accurate tool, but this has not been shown to be reliable in young children. A scale is a series of points made on a line that will be used for measurement; a mark on the far left of the line shows little pain and the mark on the far right means a lot of pain. By default the most common objective outcome measure used in pediatric studies has been the incidence and number of emetic episodes. This measure, however, correlates poorly with the somatic subjective symptom of nausea. Apfel et al have shown that 30-40% of adult patients undergoing surgery have post discharge nausea and / or vomiting while 12% have vomiting. These data on nausea in adults were based on a visual analog scale for nausea. There are no data on the incidence of postoperative nausea in children since the severity of symptoms are difficult to measure as younger children are known to be unable to use the VAS reliably. Recently a pictorial scale for measuring nausea, the Baxter Animated Retching Faces (BARF) scale, has been developed and shown to have construct, content and convergent validity as an instrument to measure nausea in children. This was a two center study that was limited to children who could speak English. The clinical usefulness of this scale in determining the incidence of postoperative and post-discharge nausea in children has yet to be determined including the lowest age where it can be used reliably, the score associated with a patient's perception of a need for treatment, the minimum change in the scores of clinical relevance and the test-retest reliability when nausea is rated as not having changed. The score has also not been validated in children who speak Spanish. This study is designed to provide the missing information and will specifically look at the Spanish speaking population.

Section D: Purpose and Objectives

This study in the pediatric Spanish speaking patient population is designed to determine: (1) The validity of the scale to measure nausea in Spanish speaking children (2) the incidence of postoperative nausea as compared to postoperative vomiting in the Post Anesthetic Care Unit (PACU) and on discharge (Post Discharge nausea and Vomiting) in this population (3) The minimal clinically relevant differences in nausea on

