Discuss the research design including but not limited to such issues as: probability of group assignment, potential for subject to be randomized to placebo group, use of control subjects, etc.

The study design is a cross sectional study of Spanish speaking patients undergoing surgery. There will be no group assignment, no placebo group and each patient will be his or her own control. Patients will receive standardized care according to the Attending Anesthesiologist's opinion of the clinical requirements for the specific situation. No changes in clinical practice or care of patients will occur solely for the purpose of the study. All patients will be asked to assess their pain and nausea using the visual analogue scales, the modified faces scale and the BARS scale as described below in the preoperative and postoperative areas. However, the order in which the scales are presented to the patient for assessment will be randomized to reduce the potential for an order effect where the patient choice of a response on one scale may influence the response on other scales. For example, having chosen a response two-thirds of the way up one scale, there will be a tendency to choose a response two-thirds of the way up the next scale.

Inclusion Criteria:

(1) Spanish speaking children (2) Age > 7 years but below 18 years (3) Elective surgery (4) American Society of Anesthesiologists physical status 1-3 (Free from major concurrent disorders) (5) Free from nausea and / or vomiting in the previous 24 hours (6) Cognitive and communicative ability to rate the intensity of symptoms as described below.

Exclusion Criteria:

(1) Inability to understand or speak Spanish (2) Developmental delay (3) Blindness (4) Impaired cognitive or communicative abilities including inability to rate the intensity of symptoms (5) Surgical procedure where vision or hearing is anticipated to be impaired in the immediate postoperative period (6) Nausea and /or vomiting within 24 hours of procedure, (7) Patient or parental refusal to participate (8) Pregnant females

F2. Procedure

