Postoperative Care: In the Post Anesthetic Care Unit (PACU) patients will receive standard care, including analgesic or antiemetic therapy as prescribed by the Attending Anesthesiologist based on his opinion of the clinical needs of the situation. When awake, the patients will be asked to rate their pain and nausea on both scales (VAS and FPS for pain, VAS and BARF for nausea). The order of presentation of scales will be the same as in the preoperative area. If a child receives analgesic or antiemetic therapy, he/she will be asked to rate the pain and nausea immediately before receiving the drug and 30-60 minutes after receiving treatment. In summary, patients will rate their pain and nausea using the VAS and the FPS-R for pain and the VAS and BARF scales for nausea at these time points: (1) before induction of anesthesia, (2) when awake in the PACU, (3) just before and (4) 30-60 mins after receiving analgesic or antiemetic therapy. The order of presentation of scales will be randomized but the same for all time points for an individual subject. After the first assessments are done in the PACU, patients will also be asked to rate their nausea on a 5 point Likert scale as: (1) Much worse than before, (2) A little worse than before, (3) The same as before (4) A little better than before and (5) Much better than before. They will also be asked if they want any treatment of their nausea. Another set of assessments will be done just prior to discharge. All other aspects of patient management will be the standard care given to such children at the Texas Children's Hospital. Patients will be discharged from the PACU when they have achieved the standard criteria set for discharge at the TCH. At the time of discharge we will give the parents a diary to record the the MAXIMUM nausea on the VAS and BARF scales and mail it back in a stamped envelope. We will phone them about 24 hours after surgery and ask if the child had any nausea, vomiting and what medications were used after going home. We will ask the parent to rate their satisfaction with the control of nausea and with the entire perioperative experience on a 0-10 scale. We will remind them to mail the nausea assessments back and to state which face represented the maximum nausea after discharge.

Section G: Sample Size/Data Analysis

G1. Sample Size

How many subjects (or specimens, or charts) will be used in this study?

Local: 240 Worldwide: 240

Please indicate why you chose the sample size proposed:

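### The change question never says which rating 'before' means, and the minimum relevant change has no named pair of scores and no rule on separating improvement from worsening

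*Combined protocol and SAP*

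**What the plan says.** Section D gives five objectives. One is "3) The minimal clinically relevant differences in nausea on" the two nausea scales, and another is test-retest reliability when nausea is unchanged.

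Section F2 (Postoperative Care) introduces the change question: "After the first assessments are done in the PACU, patients will also be asked to rate their nausea on a 5 point Likert scale". The middle options are "2) A little worse than before, (3) The same as before (4) A little better than before". No option says which occasion 'before' refers to, and the text does not say whether the question is repeated.

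The same section lists the ratings: "1) before induction of anesthesia, (2) when awake in the PACU, (3) just before and (4) 30-60 mins after receiving analgesic or antiemetic therapy". It then adds "Another set of assessments will be done just prior to discharge". So there are up to five kinds of occasion from which a change could be taken.

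Section G2 gives the analysis of the minimum relevant change in one sentence: "calculating the change in scores for patients who rated their nausea to be a little better than before or a little worse than before". For test-retest it uses "The first and subsequent scores obtained from subjects who rated their symptoms as" unchanged, with an intraclass coefficient above 0.7 as the criterion. It does not define which score is the first.

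Section F1 makes it an inclusion criterion to be "Free from nausea and / or vomiting in the previous 24 hours", and G2 itself assumes that healthy children have no nausea preoperatively.

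**The concern.** An anchor-based minimum relevant change is sound only if the child's judgement and the score difference cover the same interval. Here neither interval is stated. The child hears 'before' with no reference, and the analyst has several earlier scores to subtract. The plan also does not say whether improvement and worsening give two estimates or one, or whether changes are signed, sign-aligned or absolute.

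Section C presents the minimum relevant change as part of the missing information that the study is meant to supply, and later users would apply it to judge response. The same undefined reference also decides which children and which pairs of scores enter the test-retest analysis. If children are asked a question without a reference, later analysis cannot recover what they were comparing with.

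**Working it through.** **Figure to reproduce.** There is none. G1 sizes hypotheses 1 to 3 only and gives no number of children, precision or expected value for this analysis or for test-retest.

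**Inputs.** From the documents: the rating occasions and question wording (F2), the nausea-free criterion (F1) and the preoperative assumption (G2), a 2 cm VAS reduction as clinically important and an adult VAS SD of 2.5 cm (G1), and the 0.7 criterion (G2). Assumed here: the size of a 'little' change, the split between directions, and the SD of change.

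**Reading A: asked once, straight after the first PACU rating.** The only earlier scheduled rating is the preoperative one.

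- Change = first PACU score − preoperative score. The preoperative score is expected to be about 0, and a score cannot fall below 0. The largest possible improvement is therefore about 0, and 'a little better' has almost no valid cases. What remains is 'a little worse', which is onset of nausea.
- Children answering 'the same' would score about 0 on both occasions. With intraclass coefficient = between-child variance / (between-child + within-child variance), exceeding 0.7 needs between-child variance above 0.7/0.3 = 2.33 times the within-child variance. A group clustered at 0 has little between-child variance. The result would also say little about repeatability in children who do have nausea.

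**Reading B: asked at ratings after the first PACU one.** Take an invented child scoring 0 preoperatively, 4 awake, 6 before a drug, 4 after it and 3 at discharge. The change at discharge is:

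- from preoperative: 3 − 0 = +3
- from awake: 3 − 4 = −1
- from just before the drug: 3 − 6 = −3
- from after the drug: 3 − 4 = −1

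Both sign and size depend on a reference that the plan does not give. The child may have one rating in mind and the analyst another.

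**Direction, if signed changes were averaged over both groups.** Let each true change be m in size and w the share answering 'a little worse'. The mean is m·w − m·(1 − w) = m(2w − 1). With m = 2 cm (assumed):

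- w = 0.5: 0 cm
- w = 0.6: 0.4 cm
- w = 0.7: 0.8 cm
- w = 0.8: 1.2 cm

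Reported separately, the values would be +2 and −2 cm. With m = 1 cm the pooled values halve.

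**Absolute changes.** These avoid cancellation but absorb noise. If change is normal with an assumed SD of 2.5 cm, the mean absolute change is 1.99 cm when the true change is 0 and 2.60 cm when it is 2 cm. The handling of sign therefore has to be prespecified too.

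**The readings are alternatives.** Under A nearly all raters with a change are in the 'worse' group, so there is little to cancel. Cancellation needs B together with signed averaging.

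**The case against.** The plan can be read more kindly. The F2 sentence could mean that the question accompanies every rating after the first PACU one, which is close to what is recommended below. The G2 sentence joins the two groups with 'or' and is equally consistent with two separate estimates. Both points stand: the text is ambiguous, and no wrong analysis is prescribed. But the kinder reading still leaves 'before' without a reference and the score pair unnamed, and no other section supplies either.

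A reader might infer three stronger things that the documents do not support:

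- *That the plan pools the two directions and that they cancel.* G2 does not say that the groups are combined or that signed values are averaged. It only fails to rule this out.
- *That the minimum relevant change is taken from the first score to later ones.* G2 uses that pairing only for children reporting no change, in the test-retest analysis.
- *That an interval containing a drug is in itself a fault.* An anchor-based estimate may span treatment, and the fix below does so. The fault would be a mismatch between the interval judged and the interval scored. A drug in the interval matters more for test-retest, so such intervals should be identifiable.

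It is also fair to say that the cancellation figures rest on assumptions. The plan uses 2 cm for an important or satisfactory response to treatment, not for a 'little' change, and it gives no split between directions.

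**Conclusion.** The concern holds as an undefined reference and an undefined pair of scores, affecting the minimum relevant change and test-retest objectives. On the literal reading of F2, improvement is almost unobservable, the estimate describes onset only, and the 'unchanged' pairs sit near zero. This rests on preoperative scores being near zero, which F1 and G2 both imply. On the later-question reading, the sign and size of a child's change depend on an unstated choice. The loss from averaging both directions (0 cm at 50:50 and 0.8 cm at 70:30, instead of 2 cm each way) is conditional on signed pooling and an assumed 2 cm. It shows why the rule must be written down and is not a prediction of the result. The tests of hypotheses 1 to 4 do not use the change question and are unaffected. The change should be made before children are asked, because the missing reference cannot be supplied afterwards.

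**What to change.** - **Question (F2).** Ask the 5-point question at each rating after the first PACU rating, worded 'compared with the last time I asked you', and put this in the Spanish script.
- **Change score (G2).** Calculate change from that immediately preceding rating, so that the anchor and the score cover the same interval.
- **Reporting (G2).** Give the minimum relevant change separately for 'a little better' and 'a little worse', each beside the change in children answering 'the same'. Use confidence intervals that allow for repeated pairs within a child.
- **Test-retest (G2).** Use the same pairing for children reporting no change, and flag intervals that contain an analgesic or antiemetic.

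The cost is script and analysis wording, one extra spoken question at ratings already scheduled, smaller groups in each direction than a combined group would give, and an analysis that handles clustering. Clinical care does not change.
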